5.1 Drug Administration Training

All subjects and study partners will receive extensive training at each visit regarding home administration of IN insulin using the aerosol nasal device during visits 1 and 2 (screening and baseline, respectively). Subjects will be required to administer the dose twice daily, once in the morning and again in the evening (at least 8 hours between doses). Subjects will have the opportunity to immediately do a retrial administration if they are unsuccessful in releasing the study drug intranasally. If the aerosol nasal device is discharged prior to insertion into the nose, then a retrial admission would be indicated. However, if the device is discharged following nasal insertion, then a retrial would not be permitted. The steps to ensure that subjects maintain compliance with the study protocol over 4 weeks include administering the following:

- In-clinic training sessions: screening and baseline visits
- Phone call to assess drug compliance from study coordinator 2 weeks after baseline visit.

In addition to drug administration training, subjects will be given a daily Drug Diary to record the time and date of each self-administered dose, drug vial number and any comments for study staff. Instructions and training for the Drug Diary will be given to all subjects and study partners at the same times as the drug administration training.

5.2 Drug Administration with Aerosol Nasal Device

Each dosing administration will require the following items: a) 2 Devices each with a nose piece cover; b) Device holder; c) 10 ml vial of Regular Insulin (Novolin R); d) 2 Insulin syringes; e) alcohol wipe; f) needle clipper and/or sharps container.

During the baseline/initial treatment visit the subject/study partner will administer the study drug in front of study personnel to ensure adherence to study protocol for drug administration. To ensure safety and medication compliance, subjects will be followed-up with a routine phone call 2 weeks after

NIFT-D

baseline (safety and drug compliance) and final treatment visit (safety). Non-insulin dependent diabetic subjects will monitor their fingerstick glucose as part of routine schedule as determined by their primary clinician/endocrinologist.

Devices will be shipped to the clinical study site. One device with a nose piece cover will be supplied for each dose to be administered in the study. A kit containing the necessary items will be distributed to each subject and replaced as necessary. This will include several extra devices in case there are issues with any devices. Each device is to be loaded with a 10 unit dose of regular insulin to be used immediately with up to a maximum of 10 minutes prior to IN administration. The Nose Piece and Secondary Drug Container (temporary) are the only components of the device that will come into contact with regular insulin and subject's nasal cavity.

5.3 Device Dose Loading and Administration

1. The care partner will prepare device.

a. Remove the syringe, device and study drug. Open the device covers and place devices in device holder (Figure 5). Carefully remove the cap from the syringe needle.
 The care partner will switch to a new study drug vial every two weeks during the dosing period. Study drug vials will be prepared by staff before subject and care partner receive them. Subjects will receive two vials of medication at the first dosing visit.

2. The care partner will load the drug formulation into the devices.

- a. Remove the cap from the top of the vial.
- b. Wipe the top of the vial with an alcohol wipe.
- c. Load the 0.1 ml desired regular insulin dose volume from the vial using the Insulin syringe.
 - i. Immediately (within 10 minutes) before taking dose, load the devices with study drug.
 - ii. Pull Syringe plunger to 0.1 ml
 - iii. Insert syringe needle into the vial top, and push air into the vial
 - iv. Turn the medication vial upside-down and slowly pull the syringe plunger down, withdrawing the study drug until 0.3ml line is visible just above the plunger. Tap the syringe to move any air bubbles to the top

- v. Slowly push the plunger up to the 0.1ml line to push any air bubbles back into the vial. There should be a fluid level at the 0.1 ml line.
- vi. Turn the medication vial upright and gently pull the syringe out without moving the plunger.
- d. Insert the syringe with the needle carefully into the top of the device.
- e. Slowly depress the syringe plunger, ensuring that no dose leaks. After the plunger is fully depressed, remove the syringe with the needle carefully from the device and leave the device in the device holder.
- f. Dispose of the syringe and the needle by using a needle clipper and or in a sharps container.
- g. Repeat these steps, using another syringe for the second device.
- 3. Subject will blow their nose prior to administering the first dose.
- 4. Subject will turn the device upside down and flick the nose piece to allow the drug to concentrate at its edge as shown in the figure. This helps the subject to see if the drug is loaded prior to administration.
- 5. The research staff will provide guidance to the subject on placement for nasal administration for the first dosing.
 - a. Place the nose piece of the device comfortably in the nose as shown in the figure below.
 - b. After the initial placement, the examiner will make slight adjustments to orient the nose piece in the proper direction.
- 6. Press the activation button to administer the drug in the nasal cavity.
- 7. Steps 3-5 will be repeated for the other nostril using the second prepared device.

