Planned Duration of Treatment	4 weeks				
PRIMARY ENDPOINTS					
 Number of subjects completing the EXAMINER battery Number of subjects enrolled Total number of AEs and SAEs 					

• Total number of AEs and SAEs

SECONDARY ENDPOINTS

- Reasons for subjects failing to complete EXAMINER battery
- Number of subjects completing the study
- Number of screen failures
- Reasons for screen failure
- Number of unique subjects with an AE/SAE

EXPLORATORY ENDPOINTS

- Pre-post change in executive function and behavior (EXAMINER Battery)
- Pre-post change in Appetite and Eating Habits Questionnaire (APEHQ)

INVESTIGATIONAL PRODUCTS, DOSE AND MODE OF ADMINISTRATION

Investigational Product Regular insulin (Novolin-R) 20 IU/IN (0.1ml/10 units IN in each nostril) BI	ID
---	----

SUBJECT SELECTION

Targeted Accrual	12 subjects. We estimate a need to consent 20 subjects in order to reach
	this goal.

INCLUSION CRITERIA

- 1. Male or female subject meeting international consensus criteria for probable behavioral variant frontotemporal dementia or criteria for semantic dementia (Gorno-Tempini et al., 2011; Rascovsky et al., 2011)
- 2. Subject has a MMSE score \geq 18.
- 3. Subject is > 40 and <90 years of age.
- 4. Female subjects are post-menopausal or have a negative pregnancy test
- 5. The subject must be proficient in speaking, reading and understanding English in order to comply with procedural testing of cognitive function, memory and physiology.
- 6. Subject has a dedicated family member /caregiver, who will be able to attend all visits and report on subject's status.
- 7. Subject and family member/caregiver have both provided fully informed written consent prior to participation. In the event that subject is legally unable to provide informed written consent due to deterioration in cognitive abilities, fully informed written consent must be provided by a legally authorized representative.
- 8. Subject must have undergone a brain CT or MRI as part of receiving FTD diagnosis

EXCLUSION CRITERIA

- 1. Subject has medical history and/or clinically determined evidence of other CNS disorders including, but not limited to brain tumor, active subdural hematoma, seizure disorder, multiple sclerosis, Alzheimer's disease, vascular dementia, corticobasal syndrome, progressive supranuclear palsy, Parkinson's disease, multiple system atrophy, Lewy body dementia, normal pressure hydrocephalus, Huntington's disease, or Jakob-Creutzfeldt disease presenting as dementia.

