We proposed a pilot study of IN insulin in FTD, more specific bv-FTD and SD. The majority of clinical trials of dementia employ outcome measures that focus on memory and have greater relevance to Alzheimer's disease. For instance, the Alzheimer's Disease Assessment Scale-cognitive subscale (ADAS-cog) is a battery that is heavily-weighted toward cognitive tasks affected in Alzheimer's disease, but would be unsuitable to measure change in FTD. For this reason, we will be utilizing the EXAMINER cognitive battery (https://memory.ucsf.edu/examiner) which was developed at the University of California, San Francisco to reliably and validly assess domains of executive function—the primary cognitive modality impacted in FTD. In addition, the battery includes outcomes with respect to social cognition. EXAMINER has the following attributes: modular (separate modules testing various elements of executive function), modifiable (any standard battery can be adapted to a range of experimental and clinical situations), efficient (relatively short administration time), applicable to a broad range of individuals from different age and ethnic groups, and reliable.

We aim to evaluate the feasibility of the EXAMINER cognitive battery as a cognitive outcome measure in FTD, the ability of our Center's ability to sufficiently recruit subjects with FTD, and the safety of IN regular insulin administered 20 IU BID in bv-FTD and SD over a 4 week period. Prior studies performed in the AD population have demonstrated favorable effects of this regimen in the MCI/AD population (Craft et al., 2012).

In addition, the clinical trial will investigate exploratory outcomes related to the effect of IN insulin on executive performance as measured by the EXAMINER battery and feeding behavior as measured by Change in Appetite and Eating Habits Questionnaire (APEHQ).

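### Section 5.3, step 7 repeats only steps 3 to 5 for the second nostril and leaves out step 6, the only step that discharges a device, which conflicts with the stated 10 units in each nostril

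*Combined protocol and SAP*

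**What the plan says.** All places are in the combined protocol and SAP.

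- **Dose.** The Protocol Summary gives "20 IU/IN (0.1ml/10 units IN in each nostril", twice daily. Section 1.1 describes assessing "the safety of IN regular insulin administered 20 IU BID in bv-FTD and SD over a 4 week period".
- **Devices.** Section 5.2 lists two devices for each administration and says "Each device is to be loaded with a 10 unit dose of regular insulin".
- **Loading.** Section 5.3, step 2 covers loading the first device. Step 2g then says "Repeat these steps, using another syringe for the second device".
- **Administration.** In Section 5.3, step 3 is nose blowing, step 4 is inverting and flicking the device, and step 5 (with 5a and 5b) is placing and orienting the nose piece. Step 6 is "Press the activation button to administer the drug in the nasal cavity". Step 7 is "Steps 3-5 will be repeated for the other nostril using the second prepared device".
- **Supervision.** Section 5.1 provides training at Visits 1 and 2, a compliance call two weeks after baseline and a Drug Diary. Section 5.2 says that at the baseline visit "the subject/study partner will administer the study drug in front of study personnel to ensure adherence to study protocol for drug administration".

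**The concern.** Pressing the activation button is the only act in Section 5.3 that discharges a device, and the range in step 7 stops one step short of it. As written, the second device is loaded, inverted, flicked and placed in the other nostril, and the sequence then ends. The numbered procedure and the stated dose cannot both be followed to the letter.

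What is at stake is whether the exposure given matches the exposure described. One primary objective (Section 3.1) is the safety and tolerability of intranasal insulin, and adverse event counts are interpreted against the stated regimen. Section 5.3 is the only step-by-step administration sequence in the document. The first dose is observed to check adherence to the protocol, so this text is the standard for that check, and most later doses are given at home. The point does not touch any endpoint definition, the precision statement in Section 12.4 or any planned analysis.

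**Working it through.** **Inputs**

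- Load per device: 10 units (Section 5.2).
- Devices per administration: 2 (Section 5.2).
- Administrations per day: 2 (Protocol Summary; Section 5.1).
- Treatment period: 4 weeks, taken as 28 days (Protocol Summary; Section 5.5).
- Visit 3 window: ±5 days (Section 7.1.2; Table 1).

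**Reproducing the plan's figure**

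Dose per administration = discharges × units per device. With both devices discharged, 2 × 10 = 20 IU, which is the stated dose.

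**Counting discharges in Section 5.3 as written**

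| Step | Content | Discharges |
|---|---|---|
| 1–2 | Prepare and load both devices | 0 |
| 3 | Nose blowing | 0 |
| 4 | Invert and flick | 0 |
| 5 | Place and orient | 0 |
| 6 | Press the button | 1 |
| 7 | Repeat steps 3–5 in the other nostril | 0 |

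The total is 1 discharge, so 1 × 10 = 10 IU: 10 units in one nostril and none in the other, which is 50% of the stated dose.

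**Over the treatment period, on the literal reading**

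| Treatment length | Administrations | Stated total (× 20) | Literal total (× 10) |
|---|---|---|---|
| 23 days | 23 × 2 = 46 | 920 IU | 460 IU |
| 28 days | 28 × 2 = 56 | 1,120 IU | 560 IU |
| 33 days | 33 × 2 = 66 | 1,320 IU | 660 IU |

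Over 28 days this is 56 of 112 devices discharged. If the observed first dose is given in full and the other 55 follow the text literally, the shortfall is 55 × 10 = 550 IU, and 550 / 1,120 = 49.1%.

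**Range under assumed miss rates**

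The documents give no rate at which the second discharge would be missed, so the rates below are assumptions. Shortfall = 55 × rate × 10 IU, as a share of 1,120 IU.

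| Assumed miss rate | Shortfall | Share |
|---|---|---|
| 0% | 0 IU | 0% |
| 5% | 27.5 IU | 2.5% |
| 10% | 55 IU | 4.9% |
| 25% | 137.5 IU | 12.3% |

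**Would a missed discharge show in the records?** The Drug Diary (Section 5.1) takes time, date, vial number and comments for each dose. It has no listed entry for discharge of each of the two devices, so it would not by itself reveal a miss.

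**A wording point, with no dose conflict.** Step 3 reads "Subject will blow their nose prior to administering the first dose" yet lies inside the repeated range, so it is unclear whether it is meant to be repeated.

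**The case against.** The strongest reply is that nobody would follow the literal text. A second device that has been loaded, flicked and placed in the nose has no purpose except to be discharged, and the Protocol Summary and Section 5.2 point the same way. Section 5.1 also allows an immediate repeat attempt when drug is not released, so the protocol plainly treats release as the mark of a successful administration. Parts of step 5 describe the supervised first dose, and nothing says that Section 5.3 is the sheet used at home. For the literal shortfall to occur on every later dose, the training would have to leave out the second button press too, and nothing suggests that it does. The diary accepts comments, Section 13.8 requires a log of devices dispensed and returned, and Section 11.2.3 requires device problems to be reported.

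Most of this stands as an argument about likely impact. It supports reading the text as a cross-reference slip, and it is why the 50% figure is only a bound. It does not make the text consistent: step 7 still omits the discharge step. The repeat-attempt rule deals with failed releases, not with a press the instructions never call for. Neither the device log nor the problem reports are described as recording whether each device was discharged.

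**Conclusion.** The inconsistency is real. Followed to the letter, Section 5.3 discharges 1 of 2 loaded devices, 10 of 20 IU per administration, against a stated 10 units in each nostril. The 28-day bound is 560 of 1,120 IU, or a 550 IU shortfall (49.1%) if the observed first dose is complete. These totals assume two administrations on each of 28 days and literal compliance with the text. The true miss rate is unknown; assumed rates of 0% to 25% give shortfalls of 0% to 12.3%. Given the training and the observed first dose, the real effect is probably far below the bound. The text should still be corrected because it is an operative dosing instruction and exposure underlies the safety and tolerability objective.

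**What to change.** The sponsor should reconcile the step range in Section 5.3, step 7 with step 6, the dose in the Protocol Summary and Section 1.1, and the two-device set-up in Section 5.2. The reconciled sequence should then be used in the training at Visits 1 and 2. The same edit can make clear whether step 3 belongs in the repeated range. Which sequence is right is for the sponsor and the device company to settle. The cost is a one-line correction and its reflection in training already planned, with no new procedures, visits or data.

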5.4 Outcome Measures

Neuropsychological and behavioral batteries will be performed at baseline and visit 3 (see section 7.4 for additional details).

5.5 Study Duration

Study participation will last approximately 9 weeks, consisting of a screening visit, baseline visit, followup assessment visit and two phone call visits. Subjects will receive treatment for a period of 4 weeks. Subjects who discontinue treatment will continue follow-up measures as possible.

6 Study Population

6.1 Eligibility Criteria

6.1.1 Inclusion Criteria

- 1. Male or female subjects meeting international consensus criteria for probable behavioral variant frontotemporal dementia or criteria for semantic dementia (Gorno-Tempini et al., 2011; Rascovsky et al., 2011)
- 2. Subject has a MMSE score ≥18.
- 3. Subject is > 40 and <90 years of age.
- 4. Female subjects are post-menopausal or have a negative pregnancy test
- 5. The subject must be proficient in speaking, reading and understanding English in order to comply with procedural testing of cognitive function, memory and physiology.
- 6. Subject has a dedicated family member /caregiver, who will be able to attend all visits and report on subject's status.
- 7. Subject and family member/caregiver have both provided fully informed written consent prior to participation. In the event that subject is legally unable to provide informed written consent due to deterioration in cognitive abilities, fully informed written consent must be provided by a legally authorized representative.
- 8. Subject must have undergone a brain CT or MRI as part of receiving their FTD diagnosis

6.1.2 Exclusion Criteria

A subject will not be included for consideration in this study if any of the following criteria are met:

- Subject has medical history and/or clinically determined evidence of other CNS disorders including, but not limited to brain tumor, active subdural hematoma, seizure disorder, multiple sclerosis, Alzheimer's disease, vascular dementia, corticobasal syndrome, progressive supranuclear palsy, Parkinson's disease, multiple system atrophy, Lewy body dementia, normal pressure hydrocephalus, Huntington's disease, or Jakob-Creutzfeldt disease presenting as dementia.
- 2. Subject has medical history and/or clinically determined disorders: current B12 deficiency, chronic sinusitis, untreated thyroid disease, or significant head trauma.
- 3. Subject has history of any of the following: moderate to severe pulmonary disease, poorly controlled congestive heart failure, significant cardiovascular and/or cerebrovascular events within previous 6 months, condition known to affect absorption, distribution, metabolism, or excretion of drugs such as any hepatic, renal or gastrointestinal disease or any other clinically relevant abnormality that inclusion would pose a safety risk to the subject as determined by investigator.
- 4. Subject has had previous nasal and/or oto-pharyngeal surgery and severe deviated septum and/or other anomalies.
- 5. Subject has history of any psychiatric illness that would pose a safety risk to the subject as determined by investigator.
- 6. Subject is currently taking any medications (anticholinergics, antihistamines, benzodiazepines, barbiturates, or insulin) that are clinically contraindicated as determined by investigator.
- 7. Subject has undergone a recent change (<1 month) in their SSRI or anti-depressant medication.
- 8. Subject has current or recent drug or alcohol abuse or dependence as defined by DSM-IV TR.
- 9. Screening laboratory results that are medically relevant, in which inclusion would pose a safety risk to the subject as determined by investigator.

- 10. The subject has participated in a clinical trial investigation within 1 month of this study.
- 11. The subject has an insulin allergy.

7 Study Assessments and Procedures

A summary of study events and procedures is outlined in the Study Visit Table. Demographic, Screening, and Baseline Assessments are described in Sections 7.1.1-7.1.2, the Treatment Phase is outlined in Sections 7.1.2-7.1.4, and the safety monitoring are detailed in Section 7.1.5; details of neuropsychological assessments are outlined in Section 7.4. Note that all visits are fasting unless otherwise noted.

7.1 Demographic and Baseline Assessments

7.1.1 Visit 1: Screening (Week-2)

The following procedures will be performed at this visit:

- Obtain written informed consent from study partner and subject (or subject's legally authorized representative) prior to any study related procedures.
- Review Inclusion/Exclusion Criteria.
- Review medical history, as it pertains to inclusion/exclusion criteria, such as research diagnosis, disease severity, and course of FTD
- Obtain subject's demographic information (date of birth, gender, race, education, etc.).
- Obtain details of medications taken over the course of the last 30 days.
- Complete physical exam, including neurological exam. Collect vital signs, height and weight prior to ECG and blood draw.
- Administer MMSE
- Obtain laboratory studies
- Perform a standard 12-lead ECG.
- Serum pregnancy test in women of child bearing potential
- Study Drug administration training; Hypoglycemia rescue training
- Visit 2 will be scheduled within 2 weeks (± 5 days).

7.1.2 Visit 2: Baseline/Initial Treatment Visit (Week 0)

The following procedures will be performed at this visit:

- Review Inclusion/Exclusion Criteria.
- Collect vital signs and weight.
- Collect concomitant medication information and record AEs/SAEs.
- Neuropsychological testing with EXAMINER
- Administer APEHQ
- Administer C-SSRS
- Study Drug administration training (following testing with EXAMINER).
- Hypoglycemia rescue training.
- First dose of intranasal insulin administered
- Finger glucose stick at baseline prior to first dose, and at 15 and 30 min after first dose
- Phone visit will be scheduled in 2 weeks (± 3 days).
- Visit 3 will be scheduled in 4 weeks (± 5 days).

Amendment 3.2 August 27, 2019 Confidential

7.1.3 Phone Visit 1: Safety Check (Week 2)

- Study staff phone call to address IN insulin compliance and AEs/SAEs
- Reminder to take the last dose the night before visit 3.

7.1.4 Visit 3: Final Treatment and Safety Visit (Week 4)

The following procedures will be performed at this visit:

- Collect vital signs and weight.
- Collect concomitant medication information and record AEs/SAEs.
- Review/collect AE/SAE information
- Physical and neurological examination
- Neuropsychological testing with EXAMINER
- Administer APEHQ
- Administer C-SSRS
- Obtain laboratory studies
- Phone visit will be scheduled in 2 weeks (± 3 days).

